13.2 Subject Disposition

13.2.1 Baseline Characteristics

Demographics, medical history, baseline characteristics, and prior medications will be listed and summarised in terms of descriptive statistics: mean, standard deviation, median, and range for continuous outcomes and frequencies and percentages for categorical outcomes.

13.3 Efficacy Analysis

13.3.1 Efficacy Endpoint Analysis

The change in FVC from baseline to week 12, 24, and 36 will be calculated for each subject and summarised using the population mean and corresponding 90% two-sided confidence intervals. For early withdrawn subjects, the value representing week 24 will be calculated assuming a decline rate of 60 mL/12 weeks for the period between last visit and week 24.

As a secondary approach, a mixed model will be fitted to the FVC data collected from each time point within a subject up to week 36 or last visit if withdrawn earlier. A linear or piece-wise linear relation for the FVC decline using one or several slopes will be used to model the data depending on the actual curve shape. Model parameters will be summarised. Model will be used to assess the

Clinical Trial Protocol

Vicore Pharma AB
Trial ID: VP-C21-005

Version: 7.0
Date: 15-Sep-2021

average decline in FVC after 12, 24, and 36 weeks of treatment together with 90% two-sided confidence intervals.

The number of rapid decliners in FVC, fulfilling the withdrawal criteria during the trial, will be summarised.

FVC and FEV1 will further be summarised by visit using descriptive statistics and visualised using mean value plots (with imputation). For FVC, further a plot of the model fit, that is observed means versus the model predicted curve, will be constructed.

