13 STATISTICAL METHODS

The principal features of the statistical analysis to be performed are described in this section. A more technical and detailed elaboration of the principal features will be presented in a separate statistical analysis plan, which will be signed and approved prior to the database lock.

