13.3.4 Statistical/Analytical Issues

13.3.4.1 Missing Data

To summarise the change in FVC from baseline to week 24, missing data at week 24 will be imputed assuming a decline rate of 60 mL/12 weeks for the period between last visit and week 24. No imputation will be done for the mixed model or for the safety summaries.

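### Section 13.3.1 gives early-withdrawn subjects an FVC value at week 24 only, so the week-36 mean and 90% CI as written rest on subjects still observed and lean towards C21

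*Combined protocol and SAP*

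**What the plan says.** Efficacy over 36 weeks is a named secondary objective (Section 4.2), and FVC change over 12, 24 and 36 weeks is a secondary endpoint (Section 4.5). The first-listed analysis in Section 13.3.1 reads: "The change in FVC from baseline to week 12, 24, and 36 will be calculated for each subject and summarised using the population mean", with 90% two-sided confidence intervals. For subjects who leave early it says: "For early withdrawn subjects, the value representing week 24 will be calculated assuming a decline rate of 60 mL/12 weeks", counted from the last visit to week 24. The missing-data section (13.3.4.1) has the same scope: "To summarise the change in FVC from baseline to week 24, missing data at week 24 will be imputed". It exempts the mixed model and the safety summaries from imputation and does not mention week 36.

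Other text bears on the point:

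- **Mixed model (13.3.1).** "As a secondary approach, a mixed model will be fitted to the FVC data collected from each time point within a subject". It takes in all FVC until week 36, or until withdrawal if that comes sooner, and also yields a week-36 estimate with a 90% CI. Its form is left open: "using one or several slopes will be used to model the data depending on the actual curve shape".
- **Rapid decliners (13.3.1).** "The number of rapid decliners in FVC, fulfilling the withdrawal criteria during the trial, will be summarised".
- **Mean plots (13.3.1).** The by-visit FVC and FEV1 plots are to include imputation, but no rule is given.
- **Withdrawal (5.6.1, 5.7).** Two of the seven reasons in Section 5.7 are FVC rules. A third is failing the 12-weekly evaluation, which asks, among other things, whether other antifibrotics are needed at once.
- **Last spirometry (6.5.3).** Withdrawn subjects have one more spirometry, at Visit 15, 2-4 weeks after the last dose, and no FVC follow-up to week 36.
- **SAP (13).** Further detail "will be presented in a separate statistical analysis plan, which will be signed and approved prior to the database lock". That plan is not in the documents supplied.

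**The concern.** The protocol treats early withdrawals as too important to ignore at week 24 and charges them the natural-course rate. Every subject withdrawn before week 24 also lacks a week-36 value, and later withdrawals add to them, yet no rule supplies one. The week-24 mean then covers all subjects while the week-36 mean covers those who remain. Section 3.7 links the longer treatment to durability of response, and losing decliners between the two time points can look like durability.

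Because withdrawal depends partly on FVC decline, the subjects without a week-36 value will tend to have declined more than the rest. There is no control arm in which the same shift could cancel. At stake is a week-36 estimate that is too favourable, with a 90% CI that covers the true mean less than 90% of the time.

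**Working it through.** **1. The plan's own figure.** Section 13.1 assumes a 40 mL decline at 24 weeks, a reference of 120 mL, SD 200 mL and 55 evaluable subjects.

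- SE = 200/√55 = 27.0 mL; difference = 120 − 40 = 80 mL.
- Power = Φ(80/27.0 − 1.645) = 0.907 by the normal formula and 0.900 by the noncentral t.

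The stated 90% is reproduced. It concerns week 24 only and is not in dispute.

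**2. Formula for the week-36 bias.** Let q be the share without a week-36 value and x the extra decline by week 36 of those subjects compared with the rest. Then observed-case mean − all-subject mean = q × x. If withdrawal is unrelated to FVC, x = 0 and the bias is nil.

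**3. Inputs.** The documents give neither a week-36 SD nor a week-36 dropout rate. These are assumptions:

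- True week-36 change: −180 mL with no drug effect (3 × 60 mL), −60 mL under the planned effect (40 × 36/24).
- Base slope/error split: random-slope SD 141 mL per 24 weeks, visit-error SD 100 mL. Week-24 SD = √(141² + 2 × 100²) = 200 mL, as planned. Week-36 SD = √(211.5² + 2 × 100²) = 254 mL, so with 60 subjects SE = 254/√60 ≈ 33 mL (32 mL in the simulation).
- Predicted FVC 3.7 L; baseline % predicted N(80, 12), truncated at the entry threshold; symptoms present in 30% for the 5-10% rule; UK share 0, 25% or 50%, with half or none of the UK subjects on the 60% route; linear decline.
- Withdrawal by the two FVC rules of Section 5.7 only, with no other dropout; enrolment until 60 subjects complete week 12.

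Bias is measured against the mean of the same subjects had none been withdrawn.

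**4. Hand check.** With no effect, 50% UK and half of those on the 60% route, 6.3% are missing and they decline 333 mL more: 0.063 × 333 = 21 mL.

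**5. Simulation, base split, five UK mixes.**

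| | No effect | Planned effect |
|---|---|---|
| Missing at week 36 | 4.1-8.5% | 1.9-4.3% |
| Bias towards C21 | 14-28 mL | 7-16 mL |
| Coverage of 90% CI | about 87% to 78% | about 90% to 85% |
| CI wholly on the favourable side of the truth (nominal 5%) | 11-22% | 8-12% |

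Coverage agrees with Φ(1.645 − b/32) − Φ(−1.645 − b/32): 0.87 for a bias b of 14 mL, 0.77 for 28, 0.89 for 7 and 0.86 for 16.

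**6. Sensitivity.** Crossing three slope/error splits with the UK mixes (15 scenarios) gives 8-43 mL with no effect and 4-25 mL under the planned effect. Crossing all inputs (405 scenarios per effect) gives medians of 21 and 11 mL, with extremes of 2-76 and 1-51 mL.

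**7. Other time points.** Bias is −4 to +1 mL at week 24 under the stated rule and at most 1.5 mL at week 12.

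**8. Candidate remedies at week 36.**

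| Method | Bias, no effect | Bias, planned effect |
|---|---|---|
| Mixed model, random intercept and slope | −1 to +1 mL | −1 to +1 mL |
| Mixed model, random intercept only | 3 to 23 mL | 1 to 14 mL |
| 60 mL/12 weeks rule extended to week 36 (15 scenarios) | −7 to +9 mL | −5 to +3 mL |
| Same rule, started from Visit 15 | +1 to +9 mL | 0 to +4 mL |

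With about 10% missing for mostly unrelated reasons under the planned effect, the extended rule gave −6 mL and the observed-case mean +7 mL. A rough check of the −6: the rule charges 60 rather than 20 mL per 12 weeks. If 10% of subjects are missing for 18 weeks on average (an illustrative figure), 0.10 × 40 × 1.5 = 6 mL too much decline.

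**The case against.** The strongest reply is that week 24 is the intended focus. Section 3.7 calls 24 weeks the minimum exposure needed to study efficacy and treats the extension to 36 weeks as optional; Section 13.1 sizes the trial at week 24. An observed-case week-36 summary could be deliberate. Against that, Section 13.3.1 promises the week-36 change for every subject, and no passage says that the target is those who remain on treatment. The all-subject target used here follows that wording, but the documents do not define it formally.

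Second, the mixed model already covers week 36 and uses withdrawn subjects' earlier values. This has real weight: with random slopes it removes nearly all the bias. But it is called a secondary approach, its random effects are not stated and its time shape is to follow the data, so the text does not secure that result. The count of rapid decliners shows the losses without correcting the mean. The alternate imputations in Section 13.3.4.2 are for COVID-19 impact only.

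Third, the separate SAP may hold the rule. That stands: its absence from these documents does not show that no rule exists.

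Fourth, a reader might infer that the missing subjects are mostly steep decliners. The documents do not support that. Only two of seven withdrawal reasons are FVC rules, both also require FVC below an absolute threshold, and the simulation assumes no other dropout. With 10% unrelated dropout added (no effect, no UK subjects), FVC-driven losses were about 4 of 13.5 percentage points, although the bias hardly changed.

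A reader might also infer a false claim of efficacy. The plan sets no week-36 reference, test or success rule, so there is no such test to inflate.

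**Conclusion.** The gap is real in both sections: followed as written, the rule makes the first-listed week-36 mean an observed-case mean that leans towards C21. The direction follows from the protocol's own withdrawal rules. The size does not: the share of missing subjects who are steep decliners cannot be known from the documents.

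Under the base assumptions the bias is about 0.4-0.9 of a standard error with no drug effect (14/32 to 28/32) and 0.2-0.5 under the planned effect (7/32 to 16/32). The harm is a biased secondary estimate with an interval that covers too rarely. It should be fixed, with medium confidence in its size.

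**What to change.** Choose one of two routes in Section 13.3.1, and make 13.3.4.1 match.

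1. **Preferred.** Make the already planned mixed model the main week-36 result, with its time shape and a random intercept and slope per subject fixed in advance.
2. **Alternative.** Extend the plan's own rule: for an early-withdrawn subject, week-36 FVC = last observed FVC − 60 mL per 12 weeks from the last visit to week 36. State whether Visit 15 counts as the last visit.

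Under either route, report the observed-case week-36 mean with its n as supportive, beside the count of rapid decliners. No week-12 rule is needed. If the separate SAP already contains a week-36 rule, align 13.3.1 and 13.3.4.1 with it.

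The cost is one or two sentences and, for route 2, one derived value per withdrawn subject (about 4 of 60 in the no-effect hand-check case: 0.063 × 60 = 3.8). The week-36 figure becomes slightly less favourable. Route 2 can be modestly conservative, about −6 mL under the planned effect when dropout is unrelated to FVC; over all 405 scenarios per effect its bias ran from −15 to +17 mL.

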13.3.2 Pharmacokinetic Data

Plasma concentrations of C21 and derived pharmacokinetic parameters will be summarised by time point using descriptive statistics.

13.3.3 Biomarker Data

Biomarker data will be exploratory and the analyses data-driven. Collected data will be visualised graphically and summarised descriptively.

13.3.4 Statistical/Analytical Issues

13.3.4.1 Missing Data

To summarise the change in FVC from baseline to week 24, missing data at week 24 will be imputed assuming a decline rate of 60 mL/12 weeks for the period between last visit and week 24. No imputation will be done for the mixed model or for the safety summaries.

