3.9 Risk-Benefit Assessment

The risks to subjects in the present trial will be reduced by using C21 doses which have been evaluated in a recently completed Phase 1 trial (C21-003) (preliminary data) and found to have an acceptable safety profile; moreover centrally read telemetry data did not identify any clinically significant findings.

In addition, the risks will be minimised by strict compliance with the eligibility criteria and by close clinical monitoring. An independent data monitoring committee (IDMC) will also meet regularly to review the safety data and provide appropriate recommendations to the Sponsor on the overall safety of trial participants (see Section 14).

All subjects participating in the trial will be followed closely by medically qualified staff throughout the trial period (see Section 2 and Section 6.1). Adverse events will be carefully documented, and the subjects will receive relevant treatment should they occur.

IPF is a progressive, irreversible and fatal disease. Patients with IPF may receive benefit from stabilisation of their disease with C21.

Repetitive lung function measurement manoeuvres during the trial can lead to cough, shortness of breath, dizziness, or exhaustion, but since the subjects only carry out forced manoeuvres during clinic visits (not at home), these are always performed under medical supervision to ensure availability of medical aid if required. The assessments are part of the regular and well-established assessments for this patient population.

Furthermore, the protocol defines withdrawal criteria to secure the safety of subjects with severe progression of disease.

If the physician judges it necessary for the subject to receive a different treatment during the trial period, the subject will be withdrawn from the trial and receive relevant treatment.

Based on the above, it is considered ethically justifiable to include patients in the present trial, as the potential benefits of C21 are judged to balance possible disadvantages connected with participation in the trial.

Clinical Trial Protocol

Vicore Pharma AB
Trial ID: VP-C21-005

Version: 7.0
Date: 15-Sep-2021

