6.5.3 End-of-Trial (Visit 15)

Visit 15 is performed minimum 2 weeks and maximum 4 weeks after the last IMP administration.

The following procedures are performed:

- Recording of concomitant medication
- 12-lead ECG
- Blood sampling for safety and biomarker assessments (See [Table 1](#) and Section [8](#))
- Urinalysis
- Pregnancy test (beta-HCG)
- Physical examination including body weight (See [Table 1](#) and Section [8.2.4](#))
- Vital signs
- Spirometry
- Slit lamp examination
- Concomitant medication
- Reporting of AEs

If a subject is withdrawn from treatment (see Section [5.7](#)), a Visit 15 (end-of-trial visit) must be performed.

Clinical Trial Protocol

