13.1 Sample Size and Power Considerations

Sample size is based on assumptions of a 40 mL decline in FVC/24 weeks and a standard deviation of 200 mL. With 55 evaluable subjects there is a 90% power that the 90% confidence interval for the decline in FVC at 24 weeks exclude the value 120 mL, a value considered to represent the natural course decline in 24 weeks for an untreated subject. The total of 60 subjects will be included to compensate non-evaluable subjects for reasons such as early drop out.

Analysis Data Sets

The full analysis set (FAS) will consist of all subjects who have received at least one dose of IMP and who has at least one post-baseline assessment of efficacy.

The per protocol analysis set (PPAS) will be a subset of FAS and consist of all subjects without any major protocol deviations that are judged to compromise the analysis of the data and with data collection up to at least week 24. All protocol deviations will be judged as major or minor prior to database lock.

The safety analysis set (SAS) will consist of all subjects who have received at least one dose of IMP.

The pharmacokinetic (PK) dataset will consist of all subjects selected for PK assessments and with at least one post-dose plasma sample analysed.

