13.3.4.2 Examination of Subgroups

Important demographic and baseline value-defined subgroups may be investigated.

Subgroups or alternate imputations to investigate the impact of the COVID-19 pandemic on the analyses due to an expected increased number of subjects with missing data will also be investigated.

A detailed description will be provided in the Statistical Analysis Plan.

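### The week-24 FVC imputation needs one trigger and a defined anchor visit, and should interpolate when FVC was measured on both sides of week 24

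*Combined protocol and SAP*

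**What the plan says.** The week-24 rule appears twice in the protocol.

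- Section 13.3.1: "For early withdrawn subjects, the value representing week 24 will be calculated assuming a decline rate of 60 mL/12 weeks", applied from the last visit to week 24.
- Section 13.3.4.1: "missing data at week 24 will be imputed assuming a decline rate of 60 mL/12 weeks for the period between last visit and week 24". The same section excludes the mixed model and the safety summaries from imputation.

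The rate and the period agree. The trigger does not: the first covers early withdrawals, the second any absent week-24 value. Neither section defines the last visit.

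Spirometry does not end at week 24. Table 1 and Section 6.5.2 schedule it at weeks 28, 32 and 36, and Section 6.5.3 adds it at the end-of-trial visit: "Visit 15 is performed minimum 2 weeks and maximum 4 weeks after the last IMP administration". Section 5.7 requires that visit for every withdrawn subject.

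The week-24 change is the quantity that was powered (Section 13.1). Section 13 defers technical detail to a separate SAP, to be signed before database lock. Its text is not in the pages reviewed.

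**The concern.** A subject can lack a week-24 FVC and still be measured later. Section 13.3.1 gives that subject no imputed value; Section 13.3.4.1 does. The two sections can therefore yield different numbers of subjects and different means for the powered estimate.

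Under Section 13.3.4.1 the last visit of such a subject falls after week 24, so the projection period is negative. Read literally, the rule adds volume back to a later measurement at 5 mL/week and passes over the week-21 and week-28 readings, which carry most of the information about week 24. When true decline is slower than 5 mL/week, which is what the trial is designed to show, the result is too favourable to C21.

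There is also an open question for withdrawn subjects. Their last scheduled measurement is Visit 15, taken off drug and possibly after other therapy has begun. Section 3.9 says that if a different treatment is judged necessary, "the subject will be withdrawn from the trial and receive relevant treatment". The protocol does not say whether that FVC can be the starting point of the projection or the week-24 value itself.

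The trial is open-label with a single arm, so FVC data are visible while these choices remain open. That is a reason to settle them in advance.

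**Working it through.** **Inputs**

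- Imputation rate: 60 mL/12 weeks = 5 mL/week (Sections 13.3.1 and 13.3.4.1).
- Design: "Sample size is based on assumptions of a 40 mL decline in FVC/24 weeks and a standard deviation of 200 mL"; 40/24 = 1.667 mL/week.
- Target: "With 55 evaluable subjects there is a 90% power that the 90% confidence interval for the decline in FVC at 24 weeks" should "exclude the value 120 mL, a value considered to represent the natural course decline in 24 weeks for an untreated subject"; 120/24 = 5 mL/week, the same as the imputation rate.
- Interval: two-sided 90% (Section 13.3.1). Planned total: 60 (Section 13.1).
- Visits: weeks 21, 24, 28, 32, 36. Visit 15 for a subject treated to week 36: 36 + 2 to 36 + 4 = weeks 38 to 40.
- Share of subjects with no week-24 FVC but later data: not given. Assumed range 5 to 20%.

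**1. The plan's own figure.** n = (200 × (1.645 + 1.282)/(120 − 40))² = 53.5, rounded up to 54. With the noncentral t, 55 subjects give 90.05% power. The stated sample size is reproduced and this point does not affect it.

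**2. Literal rule with the last visit at week w.** Imputed FVC24 = FVC(w) − 5 × (24 − w). If FVC falls linearly at b mL/week, true FVC24 = FVC(w) + b × (w − 24). For w > 24 the error is therefore (w − 24) × (5 − b). A positive error means that the decline is understated.

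| Last visit | Added back (mL) | Error at b = 1.667 | Error at b = 5 | Error at b = 0 |
|---|---|---|---|---|
| Week 28 | 20 | +13.3 | 0 | +20 |
| Week 32 | 40 | +26.7 | 0 | +40 |
| Week 36 | 60 | +40.0 | 0 | +60 |
| Visit 15, weeks 38–40 | 70–80 | +46.7 to +53.3 | 0 | +70 to +80 |

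The Visit 15 row assumes that the slope does not change off drug.

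**3. Unsigned reading.** If a programmer subtracts the decline whatever the sign of the period, the week-36 case gives FVC36 − 60. The true value at the design decline is FVC36 + 20, so the error is −80 mL. The signed and unsigned readings differ by 40 − (−80) = 120 mL for the same subject.

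**4. Projecting forward from week 21.** Error = −3 × (5 − 1.667) = −10 mL.

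**5. Interpolating between weeks 21 and 28.** FVC24 = (4/7) × FVC21 + (3/7) × FVC28. At the design decline the changes from baseline are −35.0 and −46.7 mL, and the interpolated change is −(4/7) × 35.0 − (3/7) × 46.7 = −40 mL. The error is zero for any linear decline over the interval.

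**6. Effect on the mean.** Shift = share × error. From week 36 at the design decline, with 60 subjects: 3 × 40/60 = 2 mL (5%), 6 × 40/60 = 4 mL (10%), 12 × 40/60 = 8 mL (20%). If FVC is flat: 3 to 12 mL. If Visit 15 is taken as the last visit: 0.05 × 46.7 = 2.3 mL to 0.20 × 53.3 = 10.7 mL. For scale, the 90% CI half-width at SD 200 is 45.1 mL with 55 subjects and 43.1 mL with 60; the design contrast is 80 mL.

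**7. Visit 15 as anchor after early withdrawal.** Starting 2 to 4 weeks later removes 10 to 20 mL of assumed decline and substitutes the observed change over those weeks. After a stop at week 12, the imputed decline is 40 to 50 mL instead of 60 mL. The net difference is zero if off-drug decline is 5 mL/week. At a 5 to 20% share, removing up to 20 mL moves the mean by at most about 1 to 4 mL if FVC does not change off drug. After a stop at week 21, Visit 15 falls at weeks 23 to 25, so it can precede, coincide with or follow week 24.

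**The case against.** Several counter-arguments have force.

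- **Scope, not formula.** A reader might infer that the protocol holds two conflicting imputation rules. It does not. Rate and period are identical, and early withdrawals without a week-24 value are a subset of subjects missing week 24.
- **Frequency.** A reader might infer from "due to an expected increased number of subjects with missing data" in Section 13.3.4.2 that isolated loss of week-24 FVC will be common. That passage gives no rate and does not mention this pattern; it also commits to alternate imputations for COVID-19. In addition, Visit 11 is where continuation into period 3 is decided and drug is dispensed, so a continuing subject is unlikely to skip it altogether. A failed or unacceptable spirometry at Visit 11 remains possible, since curves are centrally graded (Section 8.1.1).
- **False success.** A reader might infer that the rule biases the trial towards a positive result when C21 does nothing. The documents do not support that: at the reference decline of 5 mL/week the back-cast error is exactly zero.
- **Strained reading.** The text speaks of a decline up to week 24, and Section 13.3.1 is about withdrawals, so forward projection was probably intended. That is fair, but the forward version from week 21 still replaces bracketing measurements with an assumed slope.
- **Visit 15.** A reader might infer that using Visit 15 is an error. It is a real measurement, and whether off-drug FVC counts is an estimand choice. The documents leave it open; they do not get it wrong.
- **Safeguards.** FVC is a secondary endpoint, the mixed model uses observed FVC without imputation, and the separate SAP may already settle the rule.

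These arguments keep the point small. They do not supply a definition of the last visit or a rule for week 24 missing with later data present.

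**Conclusion.** The point holds as a minor one. The two sections need a common trigger, the anchor visit needs a definition, and the method for a subject measured on both sides of week 24 can be improved at no cost. The affected value is off by tens of millilitres per subject under the literal rule at the design decline, but the likely effect on the mean is a few millilitres and would seldom decide whether the interval excludes 120 mL.

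The size rests on three assumptions: linear decline around week 24, a true rate equal to the design value, and a 5 to 20% share last seen at week 36. Only the second is stated in the protocol. The Visit 15 question is an ambiguity to be resolved, with no demonstrated direction of bias.

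**What to change.** Use one rule, worded identically in Sections 13.3.1 and 13.3.4.1 and in the SAP:

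1. Trigger: any missing week-24 FVC, whatever the reason.
2. If acceptable on-treatment FVC exists before and after week 24, interpolate linearly between the two nearest visits.
3. Otherwise, project at 60 mL/12 weeks from the last acceptable FVC at or before week 24.
4. State in advance whether the off-drug Visit 15 FVC may serve as the anchor or as the week-24 value. That is the sponsor's choice of estimand; it only has to be made and recorded before the data are analysed.

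If the separate SAP already contains such a rule, align the protocol text with it. The cost is a few sentences; no new data, visits or subjects are needed.
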